### 7.3.4. Unscheduled Healthcare Contacts/Resource Utilization

Number of days in hospital due to asthma, unscheduled healthcare resource use and number of days off work/school whilst on-treatment will be summarised separately for subjects who complete 12, 24, 36 and 52 weeks of Part C double-blind treatment.

Number of days in hospital due to asthma whilst on-treatment will be summarised by treatment group. See Section 11.6.3 for details regarding collection of days in hospital.

Unscheduled healthcare resource use due to a clinically significant exacerbation whilst on-treatment will be summarised by treatment group. In addition, total unscheduled asthma related healthcare resource use whilst on-treatment (combining healthcare contacts due to a clinically significant exacerbation and not associated with an asthma exacerbation) will be summarised by treatment group. See Section 11.6.3 for details regarding collection of healthcare resource use.

Number of days off work/school whilst on-treatment will be summarised by treatment group.

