5.3. Type and Number of Subjects

Subjects with severe eosinophilic asthma who completed the Follow Up/Exit Visit or EW Visit from either open-label study MEA115666 or 201312 will be eligible to participate in this study.

It is estimated that approximately 375 subjects with severe eosinophilic asthma from studies MEA115666 and 201312 are expected to be screened in order to randomize approximately 300 subjects 1:1 to double-blind study treatment (150 per arm). It is anticipated that approximately 120 subjects will experience a clinically significant exacerbation and meet the criteria for the Switch to Open-Label Mepolizumab treatment within Part D. The sample size calculations assume 20% of subjects will withdraw prior to the end of the double-blind treatment phase before experiencing an exacerbation. It is anticipated that approximately 120 subjects will complete the double-blind treatment period within Part C, Visit 13.

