10. STATISTICAL CONSIDERATIONS AND DATA ANALYSES

10.1. Hypotheses

The study is designed to test the superiority of continued mepolizumab 100 mg SC treatment vs. mepolizumab discontinuation (placebo). Significance tests will be performed at the two-sided 5% alpha level (one-sided 2.5%).

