10.2.1. Sample Size Assumptions

With a sample size of 300 randomised subjects (150 per arm), it is estimated that statistical significance will be declared if the proportion of subjects with a clinically significant exacerbation following withdrawal of mepolizumab is 52.5% compared to 40% for those continuing to receive mepolizumab (hazard ratio = 0.686).

If the true hazard ratio is 0.55 (corresponding to a proportion with an exacerbation following discontinuation of mepolizumab of 60.5%), then the study has a probability of 90% of observing a hazard ratio of < 0.686 and therefore the study has 90% power for declaring statistical significance on this endpoint.

The estimated event rate for subjects randomized to mepolizumab is based on interim data from study MEA115666 which suggests 40% of subjects will experience an exacerbation within one year of randomization. In study MEA115588, the observed hazard ratio for the combined treatment arms of mepolizumab 100mg SC and 75mg SC vs placebo was 0.5. A lower event rate among those discontinuing mepolizumab is expected in this study than was observed for placebo in MEA115588 because of the continuing effects of previous treatment with mepolizumab. The sample size calculations assume 20% of subjects will withdraw prior to the end of the double-blind treatment phase before experiencing an exacerbation.

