### 8.1. Adverse Events Analyses

Adverse events analyses including the analysis of adverse events (AEs), Serious (SAEs) and other significant AEs will be based on GSK Core Data Standards.

AEs occurring during the on-treatment phase will be summarised separately for each period (Parts A/B, Part C and Part D). Adverse events will be coded using the latest version of the Medical Dictionary for Regulatory Activities (MedDRA).

The number and percentage of subjects experiencing at least one AE will be summarised. Exposure adjusted rates of AEs during Part C will also be presented to account for the length of subject exposure within the double-blind treatment period. For the definition of exposure adjusted AEs, see Section 11.6.4.

The details of the planned displays are provided in [Appendix 11](#): List of Data Displays.

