### 11.3.5. Definitions of Assessment Windows for Analyses

The following assessments will be collected on a daily basis using an eDiary device: morning peak flow, usage of rescue medication (i.e. salbutamol/albutamol), asthma symptom score, frequency of awakening due to asthma symptoms requiring use of rescue medication and time missed from work/school. Part C data will be summarised in 4-weekly periods relative to the first Part C dose, as shown in the below table.

Domain	Parameter	Analysis Window 		Analysis Timepoint
		Beginning Timepoint	Ending Timepoint	
eDiary Data	morning peak flow, usage of rescue medication (i.e. salbutamol/albuterol), asthma symptom score, frequency of awakening due to asthma symptoms and time missed from work/school	6 days prior to day of first dose	Date of first dose	Baseline
		Day after day of first dose	28 days after day of first dose	Week 0-4
		29 days after day of first dose	56 days after day of first dose	Week 4-8
		57 days after day of first dose	84 days after day of first dose	Week 8-12
		85 days after day of first dose	112 days after day of first dose	Week 12-16
		113 days after day of first dose	140 days after day of first dose	Week 16-20
		141 days after day of first dose	168 days after day of first dose	Week 20-24
		169 days after day of first dose	196 days after day of first dose	Week 24-28
		197 days after day of first dose	224 days after day of first dose	Week 28-32
		225 days after day of first dose	252 days after day of first dose	Week 32-36
		253 days after day of first dose	280 days after day of first dose	Week 36-40
		281 days after day of first dose	308 days after day of first dose	Week 40-44
		309 days after day of first dose	336 days after day of first dose	Week 44-48
337 days after day of first dose	Week 52 visit date (or 364 days after day of first dose, if earlier)	Week 48-52		

- [1] Only non-missing eDiary measurements will be summarised in 4-weekly windows, see Section 11.7.2 for further details.
- [2] Day of first dose within this table referring to first dose of double-blind IP at visit C1. For subjects analysis windowing to be restricted to 364 days following first dose of double-blind IP at visit C1.

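### Hospital days, unscheduled healthcare use and days off work or school are, on the natural reading of SAP 7.3.4, summarised in subjects who complete set durations of Part C, a set selected by the exacerbations that drive these outcomes, with no all-subject exposure-adjusted summary

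*SAP*

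**What the plan says.** SAP 7.3.4 opens with one sentence covering three of the other endpoints: days in hospital due to asthma, unscheduled healthcare use, and days off work or school. While subjects are on treatment, these "will be summarised separately for subjects who complete 12, 24, 36 and 52 weeks of Part C double-blind treatment". The section then takes each measure in turn without repeating the completer condition; for example, "Number of days in hospital due to asthma whilst on-treatment will be summarised by treatment group". SAP 7.3.1 sets ITT (Part C) as the default population for exploratory efficacy, and Tables 2.47 to 2.49 in SAP Appendix 11 carry that label. One table is listed per measure. None is described as an exposure-adjusted rate.

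Days off work or school have a second rule. SAP 11.3.5 lists the daily eDiary items, among them "frequency of awakening due to asthma symptoms requiring use of rescue medication and time missed from work/school", and says that "Part C data will be summarised in 4-weekly periods relative to the first Part C dose, as shown in the below table". No completer condition is attached. SAP 7.3.3, which covers the 4-weekly eDiary summaries, omits this item, and Table 2.49 is not titled by 4-week period.

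For adverse events the SAP does allow for unequal time in Part C: "Exposure adjusted rates of AEs during Part C will also be presented to account for the length of subject exposure" (SAP 8.1, with the formula in 11.6.4).

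Protocol 5.1 and Table 3 make the move to Part D optional, at the investigator's discretion, after a clinically significant exacerbation. Protocol 5.3 expects about 120 subjects to exacerbate and meet the switch criteria, assumes 20% withdraw before an exacerbation, and expects that "approximately 120 subjects will complete the double-blind treatment period within Part C".

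**The concern.** Completing 12, 24, 36 or 52 weeks of Part C is a post-randomisation status. The main planned route out is the switch to Part D, and the switch follows the kind of event that produces hospital days, contacts and lost workdays. SAP 11.4.2 counts healthcare use as on-treatment up to the first Part D dose, so use around the triggering exacerbation is collected and classified. The subject is then absent from every later completer table, and the triggering event goes with them.

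The protocol expects more exacerbations on placebo, so the selection is likely to differ by arm. At stake is whether these three endpoints describe resource use in the randomised groups, or only in those who did well enough, or were judged well enough, to stay blinded.

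**Working it through.** **Inputs.** From Protocol 10.2.1: 150 per arm; 40% with an exacerbation on mepolizumab; hazard ratio 0.55; 60.5% on placebo; 20% withdrawing before an event; 90% power. From Protocol 5.3: about 120 exacerbating and about 120 completing. The documents give no share of exacerbators who switch, by arm or overall, so that share is varied below.

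**1. The plan's own figures.** SAP 7.3.4 states no number, so the planning counts are checked.
- Placebo proportion: 1 − 0.6^(1/0.55) = 60.5%, as stated.
- Exacerbating: 0.8 × 150 × (0.40 + 0.605) = 120.6. Withdrawing first: 0.2 × 300 = 60. Remaining: 300 − 120.6 − 60 = 119.4. These match the 120 and 120 of Protocol 5.3.
- Schoenfeld power with 120.6 events at a hazard ratio of 0.55 is 90.7%, against the stated 90%.

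The three counts add to 300 only if the 120 exacerbators are not counted as completers. The planned completers are then the exacerbation-free subjects: 0.8 × 150 × 0.60 = 72 on mepolizumab and 0.8 × 150 × 0.395 = 47.4 on placebo. On that plan, exacerbation-related use among 52-week completers is close to zero in both arms.

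**2. Partial switching.** Let p be the proportion with an exacerbation and s the share of exacerbators who switch. Ignoring other withdrawals, the share of 52-week completers with at least one exacerbation is

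(1 − s)p / [(1 − s)p + (1 − p)].

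For example, with s = 0.5, mepolizumab gives 0.20/(0.20 + 0.60) = 25.0% and placebo gives 0.3025/(0.3025 + 0.395) = 43.4%.

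| Assumed switching, placebo / mepolizumab | Placebo | Mepolizumab | Difference (points) |
|---|---|---|---|
| 0% / 0% | 60.5% | 40.0% | 20.5 |
| 50% / 50% | 43.4% | 25.0% | 18.4 |
| 80% / 80% | 23.4% | 11.8% | 11.7 |
| 100% / 100% | 0% | 0% | 0 |
| 70% / 30% | 31.5% | 31.8% | −0.3 |
| 80% / 40% | 23.4% | 28.6% | −5.1 |
| 90% / 60% | 13.3% | 21.1% | −7.8 |

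With equal switching below 100%, the absolute difference shrinks but its sign is kept. The ratio (mepolizumab/placebo) moves away from 1: 0.66 with no switching, 0.58 at 50%, 0.50 at 80%. The contrast is null when s on mepolizumab equals 1 − (1 − s on placebo) × (0.605/0.395)/(0.40/0.60). If 80% of placebo exacerbators switch, that is 54% on mepolizumab; below 54% the contrast reverses.

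**3. Hospital days, illustrative.** A simulation used the protocol rates, 20% withdrawal and switching at the next 4-weekly visit. Two further inputs are assumptions: 12% of exacerbations hospitalised and 6 days per stay. The switching chance applies at each exacerbation.

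| Assumed switching, placebo / mepolizumab | 52-week completers, mean days (placebo vs mepolizumab) | All subjects, on-treatment days per subject-year (placebo vs mepolizumab) |
|---|---|---|
| none | 0.67 vs 0.37 | 0.67 vs 0.37 |
| 50% / 50% | 0.34 vs 0.18 | 0.66 vs 0.36 |
| 100% / 100% | 0.00 vs 0.00 | 0.65 vs 0.36 |
| 80% / 40% | 0.13 vs 0.23 | 0.64 vs 0.37 |

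The completer mean depends heavily on switching, whereas the all-subject rate hardly moves. That stability owes something to the simulation, which gives every subject in an arm the same constant rate. With real differences in risk between subjects, the rate would not be perfectly stable.

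**The case against.** Several stronger readings are tempting, and the documents do not carry them.

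- **That these measures are reported only in completers.** A reader might infer this from the opening sentence of 7.3.4, and it is the natural reading. The later sentences by treatment group, the ITT default and the ITT labels leave it ambiguous. For days off, 11.3.5 contradicts it outright. This stands: the defect for days off is an inconsistency between two SAP sections. An unrestricted reading would not remove the problem, however, because raw on-treatment counts would then cover unequal follow-up.
- **That exacerbators who switch disappear altogether.** They still count at every duration they completed before switching, and exacerbators who stay on blinded treatment count throughout. The calculations above concern Week 52, the most affected of the four tables.
- **That the arm contrast will reverse.** This needs clearly more switching among placebo exacerbators, and no document gives switching by arm. Part C is double-blind and eosinophil results are withheld from sites, so known allocation should not drive the decision, although severity might.
- **That all resource use goes to zero if every exacerbator switches.** Section 7.3.4 and Table 2.48 also cover contacts not associated with an exacerbation, and those remain. The share with an exacerbation is a proxy for these endpoints.

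The harm is also limited. Tables 2.13 to 2.16 give the frequency of, and time to, exacerbations requiring hospitalisation or an ED visit in full ITT (Part C). They do not supply days, total contacts or days off. Finally, Protocol 5.4 itself warns that high discontinuation from Part C may limit assessment of the exacerbation rate, and a per-subject-year rate that stops at the switch shares that limitation.

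**Conclusion.** The concern holds in a limited form. On its natural reading, SAP 7.3.4 summarises these measures in sets selected on a status driven by the outcome; the text is ambiguous on whether anything else is intended; and no exposure-adjusted all-subject summary is specified. On the protocol's planning counts, the 52-week tables would hold almost no exacerbation-related use in either arm. Protocol 5.3 says the 120 meet the switch criteria, not that all will switch, so this is the planning extreme.

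With equal but incomplete switching, the arm difference in the share with an exacerbation falls from 20.5 points to 18.4 at half switching and 11.7 at 80%, with direction kept. A null or reversed contrast is possible only under assumed unequal switching, such as 21% on mepolizumab against 13% on placebo when 60% and 90% switch.

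These are descriptive other endpoints with no test planned in 7.3.4. No primary or secondary conclusion depends on them. The point is worth acting on because the remedy is cheap.

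**What to change.** 1. State the analysis set in 7.3.4. Make the main summary all ITT (Part C) subjects: total on-treatment days or contacts divided by total on-treatment subject-years, per arm, as the SAP does for adverse events. Use the on-treatment window of 11.4.2 for numerator and denominator of hospital days and contacts, so that the two match.
2. Keep the 12-, 24-, 36- and 52-week completer tables, if wanted, as labelled supplements. Show the number excluded at each time by arm and reason (switch to Part D, other discontinuation, withdrawal).
3. Reconcile 7.3.4 with 11.3.5 for days off work or school, and align the title of Table 2.49 with the rule chosen.

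The cost is SAP wording and a changed denominator in three tables, with no new data. The downsides are that a rate is less direct to read than a count per subject, and that follow-up still ends at the switch, so the rate describes on-treatment use only.

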#### 7.1.5.2. Exacerbation Verification Process

In order to provide an objective assessment of the circumstances linked to the clinical decision that defines asthma exacerbations, in study Part C and Part D each exacerbation recorded in the eCRF by the Investigator or designee will be verified using data from the eDiary to confirm that the exacerbation was associated with changes in peak flow, rescue medication use, nocturnal awakening due to asthma symptoms requiring rescue medication use or symptoms. In the case that an exacerbation is regarded as not associated with deterioration in at least one of these objective eDiary parameters, the investigator will be asked to provide an explanation to support the decision for defining the event as a clinically significant exacerbation. In those circumstances where the event cannot be supported by any objective assessment, the case will not be included as a clinically significant exacerbation but will be included as an investigator defined exacerbation. This verification process will be overseen by GSK clinical staff to ensure consistency. This is the same process as employed in previous Phase III mepolizumab severe asthma studies (MEA112997, MEA115588, MEA115575). This verification process is described in detail within Section 11.9.

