**Healthcare Resource Utilization**

- All unscheduled asthma-related visits to a physician's office, visits to urgent care, visits to the emergency department, and hospitalizations associated with the subject's asthma will be recorded in the eCRF.
- Healthcare resource use will be collected as unscheduled asthma-related healthcare resource use (1) associated with an asthma exacerbation, and (2) not associated with an asthma exacerbation. Additionally, healthcare resource use will be combined in order to summarise total unscheduled asthma-related healthcare resource use.
- For consistency, exacerbations separated by less than 7 days will be treated as a continuation of the same exacerbation (see above for details of further details on collapsing exacerbations)
- The number of days in hospital is collected separately for the number of days in (1) intensive care and (2) in general ward  
This information is additionally collected separately for (1) associated with an asthma exacerbation, and (2) not associated with an asthma exacerbation.  
Therefore:
  - Number of days in hospital = Number of days in intensive care + days in general ward
  - Total days in hospital due to asthma = Number of days in hospital associated with an exacerbation + Number of days in hospital not-associated with an exacerbation

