    - ii. any other increase judged by the medical monitor (or delegate) to be clinically significant

- d. Changes in Asthma Symptoms (increase in overall asthma symptom score):
  - i. as flagged by an alert in the eDiary (A symptom score of 5 for at least two of three successive days) or;
  - ii. any other change judged by the medical monitor (or delegate) to be clinically significant (e.g.  $\geq 4$  during 2 or more consecutive days when baseline is 0)

No eDiary is provided to the subject prior to visit B1; therefore this and latter process steps will not be performed on exacerbations which start within the pre-screen period or Part A of the study.

3. The medical monitor (or delegate) will review data in the eDiary 10 days prior to the event start date and 5 days post the event start date. In exceptional circumstances data from outside this window may be considered adequate evidence.
4. If sufficient evidence was available within the eDiary data the medical monitor (or delegate) will confirm that the exacerbation is “*clinically significant*” within the CRF and will tick the relevant check-box (i.e. peak flow; rescue med use; nocturnal awakenings; asthma symptoms) based on the objective evidence available.
5. For each exacerbation for which objective evidence is not available in the eDiary data the medical monitor (or delegate) will follow up with the investigator to determine if there is alternative objective data (not in the eDiary) to support it being a “*clinically significant*” exacerbation.
6. A final decision will be made by the medical monitor on whether exacerbations with no supporting eDiary data but possibly other objective data can be included as part of the primary endpoint analysis of “*clinically significant*” exacerbations.
7. If an exacerbation with no eDiary data to support it is deemed as having another source of objective evidence, the medical monitor (or delegate) will confirm that the exacerbation is “*clinically significant*” within the CRF and will update the comments section of the InForm adjudication page to clearly specify what evidence is supporting the decision.
8. In the event that the investigator is unable to provide objective evidence to support the exacerbation, then the event will be confirmed as an “*Investigator- defined*” exacerbation within the CRF. Frequencies of “*Investigator- defined*” exacerbations will be summarised within the analysis of efficacy .

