2.36.	ITT (Part C)	SHELL	Summary and Analysis of Subject Global Impression of Asthma Severity Rating (Part C)		SAC
2.37.	ITT (Part C)	SHELL	Summary of Shift From Baseline in Subject Global Impression of Asthma Severity Rating (Part C)		SAC
2.38.	ITT (Part C)	SHELL	Summary and Analysis of Clinician Global Impression of Asthma Severity Rating (Part C)		SAC
2.39.	ITT (Part C)	SHELL	Summary of Shift From Baseline in Clinician Global Impression of Asthma Severity Rating (Part C)		SAC

Efficacy: Tables					
No.	Population	IDSL / Example Shell	Title	Programming Notes	Deliverable [Priority]
Rating of Response to Therapy					
2.40.	ITT (Part C)	SHELL	Summary and Analysis of Subject Rated Overall Evaluation of Response to Therapy (Part C)		SAC
2.41.	ITT (Part C)	SHELL	Summary and Analysis of Clinician Rated Overall Evaluation of Response to Therapy (Part C)		SAC
eDiary Parameters					
2.42.	ITT (Part C)	SHELL	Summary of Daily Salbutamol/Albuterol Use (occasions/day) by 4-Week Period (Part C)		SAC
2.43.	ITT (Part C)	SHELL	Summary of Daily Asthma Symptom Scores by 4-Week Period (Part C)		SAC
2.44.	ITT (Part C)	SHELL	Summary of Awakening at Night Due to Asthma Symptoms Requiring Rescue Medication Use by 4-Week Period (Part C)		SAC
2.45.	ITT (Part C)	SHELL	Summary of Morning Peak Expiratory Flow (PEF) by 4-Week Period (L/min) (Part C)		SAC
2.46.	ITT (Part C)	SHELL	Analysis of Time to First Worsening of Asthma Defined by Daily eDiary Parameters (Part C)	Footnote: Subjects meeting at least 2 of the possible 4 criteria for worsening of asthma for at least 2 consecutive days	SAC
Number of Days in Hospital Due to Asthma					
2.47.	ITT (Part C)	SHELL	Summary of Days in Hospital Due to Asthma Symptoms (Part C)		SAC
Unscheduled Healthcare Contacts/Resource Utilization					
2.48.	ITT (Part C)	SHELL	Summary of Unscheduled Healthcare Resource Use (Part C)	Separate pages for: 1) use associated with an exacerbation 2) use not associated with an exacerbation, 3) total resource use	SAC
Number of Days off Work/School					
2.49.	ITT (Part C)	SHELL	Summary of Days Off Work/School Due to Asthma Symptoms (Part C)		SAC

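### The total of unscheduled asthma healthcare use in SAP 7.3.4 leaves out contacts for investigator-defined exacerbations and conflicts with SAP 11.6.3 and Table 2.48

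*SAP*

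**What the plan says.** Three places in the SAP describe how unscheduled healthcare use is summarised in Part C.

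- **Section 7.3.4** gives two summaries. The first is limited to verified events: "Unscheduled healthcare resource use due to a clinically significant exacerbation whilst on-treatment will be summarised by treatment group". The second is a total, built by "combining healthcare contacts due to a clinically significant exacerbation and not associated with an asthma exacerbation". The section then refers to 11.6.3 for details of how the data are collected.
- **Section 11.6.3 (Healthcare Resource Utilization)** says that the data are collected as "unscheduled asthma-related healthcare resource use (1) associated with an asthma exacerbation, and (2) not associated with an asthma exacerbation", and that "healthcare resource use will be combined in order to summarise total unscheduled asthma-related healthcare resource use". Neither statement is limited to clinically significant events.
- **Section 11.11.5.3, Table 2.48**, carries the programming note "Separate pages for: 1) use associated with an exacerbation 2) use not associated with an exacerbation, 3) total resource use". It has no such limit either.

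The status of an exacerbation that lacks support is set in Section 7.1.5.2: "the case will not be included as a clinically significant exacerbation but will be included as an investigator defined exacerbation". Appendix 9 (11.9), step 8, repeats the rule; it begins "In the event that the investigator is unable to provide objective evidence to support the exacerbation" and ends with the event being classed as investigator-defined.

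**The concern.** A quantity labelled as a total should be the sum of classes that cover everything. Section 7.3.4 pairs a narrow class (contacts for verified exacerbations) with the complement of a broader one (contacts with no exacerbation at all). Contacts for unverified exacerbations lie between the two and are dropped.

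Appendix 9 expects every reported exacerbation to meet the basic protocol definition: systemic corticosteroids, a hospital admission or an ED visit. The dropped contacts can therefore be real use of care. Verification decides which events count towards the primary endpoint. No reason is given for it to decide which ED visits count towards a total of resource use.

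There is also a reproducibility problem. Two programmers, one working from 7.3.4 and the other from 11.6.3 and the table note, could each follow the SAP faithfully and produce different totals. An admission for an unverified event could add days to Table 2.47 and be absent from the total in Table 2.48.

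**Working it through.** The plan states no figure to reproduce, and no sample size, power or event count is involved. The check compares the definitions as a partition of contacts.

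**Classes.** Every unscheduled asthma-related contact in Part C belongs to exactly one of these:

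- CS: linked to an exacerbation confirmed as clinically significant
- INV: linked to an exacerbation left as investigator-defined (SAP 7.1.5.2; Appendix 9, step 8)
- NONE: linked to no exacerbation

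**Could INV contacts fall under NONE?** No. Protocol 8.3.2.8 requires the exacerbation section of the eCRF to be completed whenever an unscheduled contact is due to an exacerbation, and this does not depend on the later verification result. SAP 11.6.3 (Exacerbations) shows that calls, visits and hospital days are held on the exacerbation record. That record also carries the clinical-significance status as a separate variable (ACAT). A programmer following 7.3.4 would filter on that status, and INV contacts would drop out.

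**The totals side by side:**

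| Source | Exacerbation part | Other part | Total |
|---|---|---|---|
| SAP 7.3.4 | CS | NONE | CS + NONE |
| SAP 11.6.3 | CS + INV | NONE | CS + INV + NONE |
| Table 2.48 note | CS + INV | NONE | CS + INV + NONE |

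**Difference:** (CS + INV + NONE) − (CS + NONE) = INV.

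The definitions agree only if INV = 0. The relative shortfall of the 7.3.4 total is INV / (CS + INV + NONE). Neither document gives a count or rate for INV, or the split of contacts between exacerbation-related and other, so no number can be put into this expression.

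**What limits INV:**

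- Deterioration in any one of four eDiary parameters is enough for confirmation, including a change that triggers no alert but that the medical monitor judges clinically significant (Appendix 9, step 2).
- Objective evidence from outside the eDiary can also confirm an event (Appendix 9, steps 5 to 7).
- Exacerbations less than 7 days apart are collapsed. The merged record is clinically significant if any component is, and its contacts are summed (SAP 11.6.3), so those contacts stay in.

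**What keeps these events elsewhere in the report:**

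- Total hospital days are the days linked to an exacerbation plus the days not so linked, without regard to verification (SAP 11.6.3; Table 2.47).
- Frequencies of investigator-defined exacerbations are to be summarised (Appendix 9, step 8).
- Table 2.1 is an overview of all exacerbations, and Listing 14 lists them.

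**The case against.** The strongest reply is that this is one loose parenthesis. Section 7.3.4 names the quantity as total asthma-related use and sends the reader to 11.6.3, where the two complementary classes are combined. The display specification agrees with 11.6.3. On that view the complete total is already specified in two places, and 7.3.4 is merely out of line.

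Much of this stands. It is a conflict of wording with a clear majority reading, and it touches no primary, secondary or safety analysis. It does not remove the point. Section 7.3.4 cites 11.6.3 only for collection while itself stating how the total is built, and no rule was found saying which section prevails. *Clinically significant* is a working term in this SAP with its own variable, so the phrase cannot be treated as filler.

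Four stronger readings are tempting, and the documents do not support them.

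- *A reader might infer that these visits and admissions vanish from the report.* They do not. Only the 7.3.4 total is affected.
- *A reader might attach a percentage by assuming a verification-failure rate and an exacerbation-related share of contacts.* Nothing in the documents anchors either input. Such a product also assumes equal contacts per verified and unverified event. Applying one failure rate to ED visits and admissions further assumes that they fail verification as often as other events.
- *A reader might infer a bias between arms.* That would need the unverified share to differ by arm. Verification is done blinded to treatment (Appendix 9), and no mechanism for a difference appears.
- *A reader might say the protocol endpoint is breached.* The endpoint only names unscheduled contacts and resource use. The statement that all asthma-related visits are recorded (Protocol 8.3.2.8) concerns data collection, not the analysis definition.

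**Conclusion.** The point holds as a defect of definition. Followed literally, SAP 7.3.4 produces an incomplete total that conflicts with SAP 11.6.3 and the note to Table 2.48. The gap is exactly the contacts for investigator-defined exacerbations.

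Its reach is one item in the tier below the secondary endpoints, summarised descriptively with no model or test. Its size cannot be computed from the documents and may be small, given the routes to confirmation and the collapsing rule. The conclusion rests on reading *clinically significant* in 7.3.4 in the sense the SAP gives it elsewhere, and on at least one unverified exacerbation in Part C having a recorded contact. If there were none, the definitions would coincide. The wording is worth correcting because the repair costs almost nothing and removes a choice that would otherwise fall to the programmer.

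**What to change.** Before unblinding, amend the sentence in SAP 7.3.4 so that the total is contacts linked to any exacerbation, whether clinically significant or investigator-defined, plus contacts linked to none. This matches 11.6.3 and Table 2.48, which need no change for this purpose. SAP 3.2 already requires decisions on the final analysis to be made before database freeze.

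Keep the summary limited to clinically significant exacerbations as the separate item that 7.3.4 already promises. The note to Table 2.48 lists no page for it, so a sub-row under use associated with an exacerbation would be a convenient place. That row is optional: the three pages already add up, since the first plus the second equals the third.

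The cost is one sentence. All the data are already collected, and no planned summary is lost.
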